3.3 Missing data

Participants who will not adhere to the intervention definition (see SAP 1.2) will be reported as missing data and excluded from final analysis. Participants with missing data about their baseline characteristics from the questionnaire will still be included in the statistical analysis of primary outcome and secondary outcome. A table with baseline characteristics will be presented as raw data without the participants with missing data from the questionnaire.

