1.2 Adherence and Protocol deviations

Definition of adherence to the intervention

Adherence is defined as participants who has a full registration of identification number (CPR number), test center site for collection of specimen and randomization to control or intervention group. Further, the participants need to complete the OPS specimen collection send for molecular testing.

Compliance is assessed based on the number and percent of subjects who have correct registration information and representative samples for RT-PCR.

Description of adherence

The adherence to the intervention will be summarized in the study flowchart and number and “% compliance” will be summarized.

Definition of protocol deviations for the trial

The participants will be excluded from final analysis if one or more of the following deviations from the testing protocol was found:

Missing identification number (CPR number), no registered test center sites or no randomization (intervention or control) registered.

Missing RT-PCR result

Description of which protocol deviations will be summarized

The number and type of protocol deviation will be registered, and number of participants removed will be summarized in figure with study flow.

2. Trial Population

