2.4 Withdrawal/Follow-up

The level of withdrawal and the missing final RT-PCR test results during the study will be tabulated. As they only had a single OPS performed, no dropouts will be expected after the intervention – beside missing data.

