3.1 Outcome definitions

The primary outcome:

- The proportion of positive SARS-CoV-2 RNA samples by RT-PCR for intervention and control group

The secondary outcome:

- SARS-CoV-2 RT-PCR cycle threshold (Ct) value
- Test discomfort on a 11-point NRS-scale
- Development of COVID-19 disease after testing
- SARS-CoV-2 detection rate for each healthcare worker
- Mallampati Score of participants being tested

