3.4 Harms

Any adverse events during or after the collection of respiratory specimens for the trial will be noted and categorized into acute bleeding or foreign body in upper airway.

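### The exclusion for an uncompleted swab or missing RT-PCR result also removes participants from the discomfort comparison, which needs no laboratory result

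*Combined protocol and SAP*

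**What the plan says.** SAP 3.3 sets the rule: "Participants who will not adhere to the intervention definition (see SAP 1.2) will be reported as missing data and excluded from final analysis". The definition it points to, in SAP 1.2, asks for full registration and adds that "the participants need to complete the OPS specimen collection send for molecular testing". SAP 1.2 then introduces its list of deviations with "The participants will be excluded from final analysis if one or more of the following deviations from the testing protocol was found", and one entry in that list is "Missing RT-PCR result". Neither section limits the exclusion to particular outcomes. The next sentence of SAP 3.3 keeps people with missing questionnaire baseline items in the primary and secondary outcome analyses, so the section is written for both kinds of outcome.

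SAP 3.1 lists "Test discomfort on a 11-point NRS-scale" as a secondary outcome, and the analysis methods give it a GEE comparison. No separate population is named for it. SAP 2.5 says the score is given directly after the test, and it is question 5 of the on-site survey in protocol Appendix 2.

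On losses, SAP 2.4 says "As they only had a single OPS performed, no dropouts will be expected after the intervention". The sentence goes on to make an exception for missing data, and the sentence before it promises a table of withdrawals and missing RT-PCR results.

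**The concern.** The protocol's randomization section discloses the arm first, and the swab follows. Failing to complete the swab is therefore a post-randomisation event. It can plausibly depend on how well the participant tolerates the procedure, and the arms differ in whether both tonsils are touched. An analysis of discomfort restricted to completed swabs with a result may then select on something close to the outcome itself.

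There is also a simpler loss. A participant whose tube goes astray, or whose sample yields no result, has already given a valid discomfort score. The rule discards it for a reason unrelated to discomfort. NRS discomfort is the plan's main measure of what adding the tonsils costs the participant, so it should not inherit a restriction that only the PCR-based outcomes need.

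**Working it through.** **1. Does the rule reach the discomfort outcome?**
- SAP 1.2 and 3.3 refer to a single final analysis, with no outcome singled out.
- SAP 3.3 speaks of primary and secondary outcomes together.
- NRS is a secondary outcome with no population of its own.

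As written, yes.

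**2. Does the outcome need what the rule requires?** NRS is scored on site immediately after the swab (SAP 2.5; Appendix 2). It does not need a laboratory result. It does need the allocated arm and the test center, because the regression models compare arms and adjust for center.

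**3. The plan's own figures** (protocol, Sample size). Reading the 25% improvement as relative, 20% v 25% positive, with a two-sided 5% level, 80% power and no continuity correction, gives 1,094 per arm and 2,188 in total. This matches the plan. The target is 2,188 × 1.10 = 2,406.8, or 2,407. The sample size is not in question here.

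**4. Size of a possible bias.** Let f₁ and f₀ be the fractions excluded for abandoned swabs in the tonsil and control arms. Let g be the NRS gap between abandoned and completed attempts, taken as equal in both arms.

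- The full-arm mean is the completer mean + f × g.
- The difference between arms is therefore understated by g × (f₁ − f₀).

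The documents give neither f nor g. With g assumed to be 3 to 5 points:

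| Excess f₁ − f₀ | Extra abandoned swabs (of 2,407/2 ≈ 1,203) | Understatement, NRS points |
|---|---|---|
| 0 | 0 | 0 |
| 1% | about 12 | 0.03 to 0.05 |
| 5% | about 60 | 0.15 to 0.25 |

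For scale, with an assumed SD of 2.5 and clustering ignored, the standard error of the difference is 2.5 × √(2/1,094) = 0.107. A 1% excess is then 0.03/0.107 = 0.28 to 0.05/0.107 = 0.47 standard errors. A 5% excess is 0.15/0.107 = 1.4 to 0.25/0.107 = 2.3. If abandonment were more common in the control arm, the sign would reverse.

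**5. Precision if losses are unrelated to tolerance.** There is no bias. If all of the roughly 10% lost had usable scores, the standard error would be √(2,407/2,188) = 1.049 times what it need be, about 5% wider. This is an upper limit. Participants with no arm or center registered could not enter the model anyway, and some who abandon the swab will not answer question 5.

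**6. Could the final report show the problem?** SAP 1.2 plans to count deviations by type in the flow figure, and SAP 2.3 separates registration losses from missing results. An abandoned swab and a laboratory loss both count as a missing result, however. Reporting by arm is not specified, and the field list in Appendix 3 shows no item for an abandoned attempt.

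**The case against.** The strongest reply is that abandoned swabs may be rare. Staff have at least three months' experience and pass an assessed training program (Quality assurance), and both techniques are already in routine use (Ethics and safety considerations). The 10% allowance in the protocol covers dropout and missing data in general, so it is not evidence of abandonment. This stands. The bias could be negligible, and the upper rows of the table are illustrations rather than forecasts. The plan also tabulates withdrawals and missing results, so losses are counted even though a failed attempt is not named.

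Two stronger readings are tempting but not supported.

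- **Harms.** A reader might infer that harmed participants vanish from the harms summary. SAP 3.4 says "Any adverse events during or after the collection of respiratory specimens for the trial will be noted and categorized into acute bleeding or foreign body" and goes on to name the upper airway. It is not tied to adherence, to an RT-PCR result or to the final analysis set. Harm is not an exclusion criterion either: someone who bleeds but has a completed swab and a result stays in. What can be said is only that SAP 3.4 names no denominator.
- **Primary outcome.** A reader might infer that dropping failed attempts contradicts the intention-to-diagnose handling of inconclusive results. That handling applies where a test result exists. SAP 3.1 defines the primary outcome as the proportion of positive samples, so detection per sample obtained is the stated target. Preferring detection per person allocated is a choice of estimand. With an assumed 5% v 1% abandoned, it would give 0.25 × 0.95 − 0.20 × 0.99 = 3.95 points rather than 5, but nothing in the documents supports those rates.

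**Conclusion.** The point holds for NRS discomfort only. As written, the SAP removes valid discomfort scores because of a condition that this outcome does not need, and the removal can depend on tolerance after the arm is known. That the rule applies to NRS follows from the text of SAP 1.2 and 3.3. The size of the effect does not, because the abandonment rate, the NRS gap and the NRS SD are all assumed. On those assumptions it runs from nothing, through less than half a standard error at a 1% excess, to about 1.4 to 2.3 standard errors at 5%. The sample size and the primary analysis as defined are unaffected. The change is worth making because it is nearly free and removes the question.

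**What to change.** - In SAP 1.2 and 3.3, limit the completed-swab and missing-RT-PCR exclusions to the primary and Ct analyses.
- Analyse NRS discomfort in all randomised participants with a swab attempted and an NRS score, by allocated arm, whether or not a result exists.
- Report missing results by arm and by reason, separating abandoned swabs from laboratory and registration losses.
- Optionally, add a sensitivity analysis of the primary outcome that counts abandoned attempts as not detected.

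The cost is SAP wording, one reason field in REDCap and, if the optional analysis is adopted, one extra model run. No participants or procedures are added. The NRS denominator will differ slightly from the primary one and should be stated. The change recovers only the scores that are actually given, so anyone who abandons the swab and leaves question 5 blank remains missing.

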3.4 Harms

Any adverse events during or after the collection of respiratory specimens for the trial will be noted and categorized into acute bleeding or foreign body in upper airway.

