After enrollment, the participants will be randomized in a 1:1 ratio having either oropharyngeal swab performed including the posterior oropharyngeal wall and both palatine tonsils (intervention group) or only including the posterior oropharyngeal wall and avoiding the palatine tonsils (control group), see Figure B.

A block randomization list was generated by [name] using an online randomization software⁽⁷⁾ afterward uploaded to REDCap. The randomization group will be disclosed in connection with trial registration in REDCap using the REDCap “randomize” function. The oropharyngeal sample will afterward be performed by the trained healthcare workers with or without the palatine tonsils depending on the randomization to either the intervention or control group.

Figure B. Study flowchart.

The swabs will be placed in separate tubes dry and sent to the clinical microbiology laboratory for detection of SARS-CoV-2 by single-target RT-PCR at Statens Serum Institute. Samples with viral cycle threshold (Ct) values below 38 are considered positive, 38-40 inconclusive and above 40 negative⁽⁸⁾.

All participants are required to fill out a survey on-site about their reason for being tested, prior Covid-19 infection(s), vaccinations status, symptoms, and if any prior tonsillectomy has been performed (appendix 2).

All healthcare workers participating in the data collection have been given a unique ID which will be registered for each OPS performed in the study. Further, the healthcare worker will also be asked to rate the Mallampati score of the participants including in the study (appendix 5).

All data will be documented on-site in a secure web database (REDCap, appendix 3).

Outcomes

The primary outcome will be reported as:

- SARS-CoV-2 RNA by RT-PCR test result (positive, negative, inconclusive)

The secondary outcome will be reported as:

- SARS-CoV-2 RT-PCR cycle threshold (Ct) value
- Test discomfort on a 11-point NRS-scale
- Development of COVID-19 disease after testing
- SARS-CoV-2 detection rate for each healthcare worker
- Mallampati Score of participants being tested

Sample size

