Planned subgroup analyses

We planned to do a sensitivity analysis using a lower cycle threshold (Ct) < 25 for positive SARS-CoV-2 definition to explore the consequences of a higher test specificity for the SARS-CoV-2 detection rate between specimen types. We also plan to estimate the sensitivity and specificity using Bayesian latent class analysis for accounting for an imperfect reference standard. Further, we planned to do subgroup analyses exploring the distribution of positive test results for participants stratified by symptoms, previous COVID-19 infection, vaccinations status, prior

tonsillectomy and Mallampati score. To explore a potential bias from the distribution of the inconclusive test results, we excluded the inconclusive results in a subgroup analyses.

Quality assurance

All the healthcare workers who will be including participants for this study will be trained and have at least three months prior experience in oropharyngeal swabs. Further, they will complete a special standardized training- and certification program taught by a board-certified otorhinolaryngologist to ensure all healthcare workers perform the same technique on the participants in the intervention and control group. A two-hour long training session will cover the theoretical and practical part of oropharyngeal sample techniques and the study design with following elements:

- A walk-through of the practical study setup and how participants are enrolled, and diagnostic interventions are performed
- Theory on oropharyngeal swabbing including upper airway anatomy and anatomical variations/Mallampati Score.
- Practical exercises in oropharyngeal swab technique.

Checklists outlining the two different sampling techniques for oropharyngeal swabs with and without palatine tonsils, respectively, will be used to assess the swab performance of all the healthcare workers by a board-certified otolaryngologist or special trained nurse before study enrollment (see appendix 1).

An on-site healthcare professional is in charge of internal daily quality assurance ([name]).

Follow-up

The participants enrolled in the study will be asked to agree to be contacted in case of a positive test result. About one month after a positive test results the participants will receive an online questionnaire or phone call to follow up. The follow-up questions can be found in appendix 3.

Ethics and safety considerations

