Appendix 2: Survey for participants

Survey to be filled out by participant

1. Are you vaccinated against COVID-19?

YES

NO

2. Have you previously been infected with COVID-19?

YES

NO

3. Please indicate your reason for getting tested today:

Symptoms

Close contact

Positive quick test

Screening

Test ahead of social gathering or nursing home visit

Other

If 'yes' to symptoms, which symptoms do you have?

Sore throat

Headache

Cough

Muscle and joint pain

Fever

Fatigue

Reduced sense of smell or taste

If "yes" to symptoms, for how many days have you had symptoms?

Indicate number of days: _____ day(s)

4. Have you had your tonsils removed??

YES

NO

5. On a scale from 0-10, how uncomfortable was today's test for COVID-19?

No discomfort

Worst possible discomfort

To be filled out by personnel:

REDCap ID: _____

Personnel ID: _____

Participant's Mallampati score:

1

2

3

4

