Appendix 3: REDCap database

REDCap-ID	
Date	DD-MM-YYYY
Randomization	Oropharyngeal swab including palatine tonsils Oropharyngeal swab excluding palatine tonsils
CPR-number	
Sample ID	
Are you vaccinated against COVID-19?	YES NO
Have you previously been infected with COVID-19?	YES NO
Please indicate your reason your reason for getting tested today	Symptoms Close contact Positive quick test Screening Test ahead of social gathering / visit to a nursing home Other
If "YES" to symptoms, what symptoms do you have?	Sore throat Headache Cough Muscle and joint pain Fever Fatigue Reduced sense of smell or taste
If "YES" to symptoms, for how many days have you had symptoms?	
Have you had your tonsils removed?	YES NO
On a scale from 0-10, how uncomfortable was today's test for COVID-19?	0 1

	2 3 4 5 6 7 8 9 10
Personnel ID	
Participant's Mallampati score	1 2 3 4
FOLLOW UP	
Have you since the test and until four weeks later had symptoms of COVID-19?	YES NO
If 'yes' to symptoms, when did you develop symptoms?	I had symptoms when I got tested I developed symptoms 1-3 days after the test I developed symptoms 3-5 days after the test I developed symptoms 5-7 days after the test I developed symptoms 1-2 weeks after the test I developed symptoms 2-3 weeks after the test I developed symptoms 3-4 weeks after the test I do not know / I do not wish to disclose
If 'yes' to symptoms, which symptoms did you develop?	Sore throat Headache Cough Muscle- / joint pain Fever Fatigue Reduced sense of smell / taste Other
If 'yes' to fever, what was your highest temperature?	

If 'yes' to fever, how many days did you have a fever for?	
If 'yes' to symptoms, how many days did you have symptoms in total?	
Think about period from one week before your test until four weeks after. Which of the following statements describes best how you felt at your worst?	
I had no symptoms
 
I was sick and stayed home
 
I was admitted to the hospital due to COVID-19

Have you taken days off work / from school during your infection with COVID-19?	
No, I have not taken any days off
 
Yes, I have taken days off between one week before the test until four weeks after
 
Yes, I have taken days off later than four weeks after
 
Not relevant

If 'yes' to having taken days off, how many days have you taken off in total?	
Do you smoke?	
Yes
 
No
 
I used to smoke, but I do not smoke anymore
 
Not relevant / I do not wish to disclose

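### SAP 3.4 promises to note any adverse event but gives two categories only, and no form shown has a field for one, so harms would rest on unprompted noting

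*Combined protocol and SAP*

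**What the plan says.** SAP 3.4 is the only text on recording harms. It covers "Any adverse events during or after the collection of respiratory specimens for the trial", and says that these "will be noted and categorized into acute bleeding or foreign body in upper airway". It does not say who records an event, on which form, until when, or how events are summarised by arm.

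The protocol's randomization section says where data go: "All data will be documented on-site in a secure web database (REDCap, appendix 3"). The staff part of the Appendix 2 survey, headed "To be filled out by personnel", holds three items: REDCap ID, personnel ID and Mallampati score.

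On later contact, the protocol's Follow-up section says: "The participants enrolled in the study will be asked to agree to be contacted in case of a positive test result". It continues: "About one month after a positive test results the participants will receive an online questionnaire or phone call to follow up". The follow-up items in Appendix 3 begin with "Have you since the test and until four weeks later had symptoms of COVID-19" and go on to symptom timing and severity, days off, smoking, physical activity and chronic illness.

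Discomfort on a 0-10 scale is collected on site from both arms. It is a secondary outcome and is compared between arms by GEE (SAP 3.1).

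**The concern.** The promise is wide: any event, during or after collection. The means shown are narrow: two categories, no field, and later contact with a minority who are asked about something else.

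The arms differ only in whether the palatine tonsils are swabbed, so safety bears on the choice of technique. If no one has to answer yes or no for each participant, a report of no harms could reflect either a clean record or an unasked question. An event that is neither bleeding nor a foreign body may be noted, but has no category to go into.

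**Working it through.** **1. Promise against means of recording.**

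| Element of SAP 3.4 | What the forms shown provide |
|---|---|
| Any adverse event | Two categories, no option for other events |
| During collection | No field in the Appendix 2 personnel box or the Appendix 3 list; staff are present and could note an event unprompted |
| After collection | No end of window; scheduled contact for consenting test-positives only, with no question on harm from the swab |

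Appendix 4 was not in the text available, so the statement is that no form shown has the field, not that none exists.

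**2. The plan's own assumptions.** The protocol's sample size section gives 20% positive, a 25% improvement, 80% power and a 5% level. Reading the improvement as relative, 0.20 × 1.25 = 0.25. The two-sided formula for two proportions without continuity correction is

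n per arm = [z(0.975)·√(2p̄(1−p̄)) + z(0.80)·√(p₁(1−p₁) + p₂(1−p₂))]² / (p₂−p₁)²

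With p₁ = 0.20, p₂ = 0.25 and p̄ = 0.225 it gives 1,094 per arm, or 2,188 in total. This matches the protocol.

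**3. Reach of the later contact.** Expected number eligible = n per arm × proportion positive.

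- At 20% and 25%: 1,094 × 0.20 ≈ 219 and 1,094 × 0.25 ≈ 274. The unrounded total is 492 of 2,188 (22.5%), so about 77.5% have no scheduled contact.
- At 13% (the October 2022 figure in the protocol) and 13% × 1.25 = 16.25%: 142 and 178, together 320 of 2,188 (14.6%), so about 85.4% have none.

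These assume that every positive agrees and responds; the real reach would be lower.

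**4. What a complete on-site record would give.** If each of 1,094 participants in an arm had an explicit entry and all were negative, the one-sided 95% upper bound would be 1 − 0.05^(1/1094) = 0.0027, or 0.27%. The bound needs a known denominator, which blank records do not supply.

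**5. Could restricted follow-up distort the arms?** The documents give no rate for late events, so assume rates equal in both arms, full response, and every harm volunteered although nobody asks. Events seen = number eligible × rate.

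| Assumed late-event rate | True events per arm | Seen, control | Seen, intervention |
|---|---|---|---|
| 0.1% | 1.1 | 0.22 | 0.27 |
| 0.5% | 5.5 | 1.1 | 1.4 |
| 1% | 10.9 | 2.2 | 2.7 |

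The difference is under one event throughout. With equal positivity (20% in each arm) it is zero.

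**The case against.** The strongest case against the point is that harms text this short is proportionate. The protocol's ethics section says that both techniques are already in use in the Danish healthcare system and add no risk beyond that of a regular test. A trained worker is present at every swab, the two named categories are mainly immediate events, and SAP 3.4 commits to noting any event. Tolerability is not ignored, because the discomfort score is collected and compared in both arms. All of this stands, and it keeps the point small. It does not supply an entry for each participant or a place for other events, and a 0-10 score does not record a discrete event.

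A reader might go further in three ways that the documents do not support.

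- **That the harms result is bound to be near zero.** Staff can note acute events for anyone, so under-recording is possible but zero is not forced. Nor do the documents plan a between-arm comparison of harms that could be defeated.
- **That harms would be captured unevenly, 1.25 times as often in the tonsil arm.** The ratio 25% / 20% is only eligibility for a follow-up that does not ask about swab harms, and it restates the assumed effect on positivity. The working shows a difference of under one event even on generous assumptions.
- **That late events can be learned only from test-positives.** Spontaneous reports do not depend on scheduled contact.

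**Conclusion.** The point holds as a gap in how harms are collected. On the forms shown, recording is unprompted, a blank cannot be told apart from no event, and events outside the two categories have no label. Scheduled later contact would reach about 14.6% to 22.5% of participants under the positivity figures above and would not ask about swab harm.

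It is a minor improvement. Harms are neither a primary nor a secondary outcome, and nothing here affects the sample size, the primary analysis or the discomfort comparison. The conclusion rests on Appendices 2 and 3 being the forms in use; an adverse-event field in material not available here would remove most of it.

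**What to change.** - **Forms.** Add one mandatory line to the Appendix 2 personnel box and to REDCap, completed for every participant at the swab: adverse event none / bleeding / foreign body / other (specify).
- **SAP 3.4.** Define the reported window as the test visit. Give counts by arm, with the number of participants who have a completed entry as denominator. List later spontaneous reports descriptively.

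The cost is a form line, a few sentences and seconds per participant. Two limits remain. Late events are described rather than compared. Staff who make the entry also know the arm, because allocation is disclosed at registration before the swab; a mandatory entry reduces room for selective noting but does not remove it.
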